6.1 General Study Design and Plan

The project uses a non-randomized pilot study to establish the relevance, feasibility and usability of the online Mindfulness program for community-dwelling stroke survivors and their caregivers.

Fig. 1. Flow chart

6.2 Inclusion-Exclusion Criteria and General Study Population

Stroke survivors and caregivers are purposefully selected to be representative of individuals who have had a stroke and caregivers (wide range of impairments, familiarity with computers, age, sex, gender, ethnicity, race and socio-economic backgrounds).

Inclusion criteria:

- Aged older than 18 years old
- Diagnosis of stroke (for stroke survivors)

- Ability to access Internet using a computer, a tablet and/or a smartphone
- Ability to provide informed consent
- Fluent in English

Exclusion criteria:

- Severe language impairments
- Regular meditation or full participation in a mindfulness program within past 3 months

6.3 Study Assessments

Table 1. Outcome measures at each time point

Visit	Baseline	Post-intervention	Follow-up
Target day of visit	1	22	52
Protocol assessment time windows (days)	1	± 2	± 7
Participant characteristics	x		
SIS*	x	x	x
HADS	x	x	x
NIH PSS	x	x	x
Sleep Quality	x	x	x
WHOQOL-BREF†	x	x	x
Zarit Burden Inventory†	x	x	x
PSSUQ		x	
Qualitative semi-structured interview		x	
Adverse event monitoring	x	x	x

* Stroke survivors only

† Caregivers only

The SIS 3.0 includes 59 items organized in 8 domains about the impact of stroke on health and life. Each question is scored from 1 (severe difficulty) to 5 (no difficulty) and each domain score is normalized. Higher scores indicate lower perceived impact of stroke. Participants also rated their perceived recovery on a sliding scale from 1 (no recovery) to 100 (full recovery).

The HADS is a 14-item scale with 7 items each for anxiety and depression subscales. Each item is scored from 0 to 3, with higher scores indicating higher anxiety or depressive symptoms.

The NIH PSS includes 10 items about the occurrence of life stressors scored from 0 (never) to 4 (very often). Higher scores indicate higher perceived stress.

The Single-item Sleep Quality includes an 11-point visual analogue scale about sleep quality in the past week (0: poor, 10: excellent sleep quality).

The WHOQOL-BREF comprises 26 questions from 4 domains about health and well-being. The scores

are normalized, and higher scores indicate better perceived health and well-being. The Zarit Burden Interview includes 22 questions about caregiver burden rated from 0 (never) to 4 (nearly always). Higher scores indicate higher perceived burden.

The adapted PSSUQ consists of 5 questions on perceived satisfaction with the website. Each question is scored on a 7-point Likert scale from 1 (Strongly Agree) to 7 (Strongly Disagree). Higher scores indicate lower usability.

7. Sample Size

A convenience sample of 10 stroke survivors is targeted to capture the relevance, feasibility and usability of the Mindfulness Program and to obtain data saturation and richness on the qualitative semi-structured interviews. This study is not powered to detect differences in quality of life or psychological well-being.

8. General Analysis Considerations

8.1 Timing of Analyses

- The qualitative analysis will be performed by 2 members of the research team after each interview have been transcribed verbatim.
- The final analysis will be performed when qualitative data saturation will be achieved and a sample of 10 stroke survivors have completed the intervention.

8.2 Analysis Populations

8.2.1 Full Analysis Population

- All participants who complete the intervention.

8.2.2 Safety Population

- All participants who received the intervention but excluding participants who drop out prior to receiving any treatment.

All outcomes will be presented using descriptive statistics; normally distributed data by the mean and standard deviation (SD) and skewed distributions by the median and interquartile range (IQR). Binary and categorical variables will be presented using counts and percentages. JASP version 0.14.1. will be used for all statistical analysis.

The subsections below will describe analyses in addition to the descriptive statistics.

The results of the adapted PSSUQ will be averaged for each group. For each group, differences prior to, after the mindfulness program and at 1-month follow-up will be assessed using a repeated measure analysis of variance (ANOVA). If data normality is violated, data will be transformed, or non-parametric statistics will be substituted. The semi-structured interview will be transcribed verbatim and analyzed independently using thematic content analysis by 2 members of the research team to identify codes, themes and overarching categories, using the Braun & Clarke six-step framework for inductive thematic analysis.

9. Summary of Study Data

Participant characteristics and the mean scores for each self-reported measure will be summarized in a table format.

A figure will be created with individual data and mean data for each outcome measure.

All continuous variables will be summarized using the following descriptive statistics: n (sample size), mean and standard deviation. The percentages (based on the sample size) of observed levels will be reported for all categorical measures.

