5.2 Endpoints

Stroke survivors:

- Change in Stroke Impact Scale (SIS): quality of life and impact of stroke (primary, post-intervention)
- Change in Hospital Anxiety and Depression Scale (HADS): anxiety and depression (secondary, post-intervention).
- Change in NIH Perceived Stress Survey (NIH PSS): perceived stress (secondary, post-intervention).
- Change in Single-Item Sleep Quality Scale: Sleep quality (secondary, post-intervention).
- Post-Study System Usability Questionnaire (PSSUQ): Usability of the online platform used to host the intervention (secondary, post-intervention).

Caregivers:

- Change in World Health Organization Quality of Life-BREF (WHOQOL-BREF): quality of life (secondary, post-intervention).
- Change in Zarit Burden Interview: perceived burden (secondary, post-intervention).
- Change in Hospital Anxiety and Depression Scale (HADS): anxiety and depression (secondary, post-intervention).
- Change in NIH Perceived Stress Survey: perceived stress (secondary, post-intervention).
- Change in Single-Item Sleep Quality Scale: Sleep quality (secondary, post-intervention).
- Post-Study System Usability Questionnaire (PSSUQ)

All outcome measures are administered at 3 time points: pre-intervention, within 48 hours of the end of the intervention and at 1-month follow-up (+/- 1 week). All outcome measures are administered via REDCap. A qualitative semi-structured interview is also conducted post-intervention to capture satisfaction and usability of the mindfulness intervention.

Safety outcomes

[figure not shown]
Adverse events are reported at each meeting. Participants are asked about any change in their medical status or hospitalization, since the last meeting.

6. Study Methods

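### The secondary change scores (8 endpoints as listed, 13 scores if subscales and domains are split) go to unadjusted significance tests with no alpha, order, exploratory label or confidence interval, although the aim is only to estimate

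*SAP*

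**What the plan says.** SAP 5.2 makes change in the Stroke Impact Scale (SIS) the only primary endpoint. The secondary change endpoints are:

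- **Survivors:** HADS, NIH Perceived Stress Survey and single-item sleep quality (3).
- **Caregivers:** WHOQOL-BREF, Zarit Burden Interview, HADS, NIH Perceived Stress Survey and single-item sleep quality (5). A typical entry reads "Change in World Health Organization Quality of Life-BREF (WHOQOL-BREF): quality of life (secondary, post-intervention".

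SAP 6.3 describes two of these instruments as having several parts: "The HADS is a 14-item scale with 7 items each for anxiety and depression subscales", and "The WHOQOL-BREF comprises 26 questions from 4 domains about health and well-being". It describes no total score for either.

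The inferential plan is one sentence in the methods text under 8.2.2: "For each group, differences prior to, after the mindfulness program and at 1-month follow-up will be assessed using a repeated measure analysis of variance". The same text presents this as an addition to the descriptive statistics, so testing is intended. The sentence names no outcomes. The natural reading is that it covers every measure taken at all three visits. The usability questionnaire (PSSUQ) is only averaged.

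On purpose, SAP 5.1 sets the second objective as estimating possible short-term impact, and section 7 states: "This study is not powered to detect differences in quality of life or psychological well-being". The protocol's Phase 2 text says these measures are collected to guide a future intervention study, including through the program's preliminary effect.

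**The concern.** A plan that aims to estimate should deliver estimates with their uncertainty. This one delivers a set of omnibus F tests, and no rule says how the resulting p-values are to be read. An F test over three visits does not give the size of the change from baseline to post-intervention, which is how 5.2 defines the endpoints.

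With 8 or 13 such tests in groups of about 5 to 10 people, some will probably cross a conventional cut-off by chance. A chance result could then be described as a benefit on anxiety, depression, stress, sleep, burden or quality of life, and could influence the choice of outcome for the next study. Caregivers are the more exposed group: all their change endpoints are secondary, and they have the larger number of scores.

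**Working it through.** The documents state no error rate, so there is no figure to reproduce.

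**Count of tests**

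- As listed in SAP 5.2: 3 + 5 = 8.
- By score, using the instrument descriptions in SAP 6.3:
  - survivors: HADS 2 + stress 1 + sleep 1 = 4;
  - caregivers: WHOQOL-BREF 4 + Zarit 1 + HADS 2 + stress 1 + sleep 1 = 9;
  - total: 13.
- Left out: SIS (primary), PSSUQ (averaged only) and any pairwise follow-up comparisons.

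**Inputs from the documents:** three visits (SAP 6.3, Table 1), 10 survivors (SAP 7) and 5 to 10 caregivers (protocol abstract).

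**Assumptions:** 5% per F test; no true change; equal correlation between scores within a group, shown over a range; survivors and caregivers independent; constant correlation between visits. With constant correlation the stable person effect cancels out of the F ratio, so its size does not matter.

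**Independent scores, by formula**

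- Any significant result, better or worse, in k tests: 1 − 0.95^k. For k = 13 this is 48.7%; for k = 8 it is 33.7%.
- False improvement means a significant F test with a post-intervention mean better than baseline. Under the null, half of the significant results point that way, so the rate per test is 2.5%. For k = 13: 1 − 0.975^13 = 28.1%. For k = 8: 1 − 0.975^8 = 18.3%.

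**Correlated scores, by simulation** (three-visit repeated-measures ANOVA under the null, 10 per group)

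| Family | Correlation | Any significant | False improvement |
|---|---|---|---|
| 13 scores | 0 | 49% | 28% |
| 13 scores | 0.5 | 40% | about 23% |
| 13 scores | 0.8 | 28% | 15% |
| 8 endpoints | 0.5 | 30% | 16% |
| Survivors, 4 scores | 0.5 | 16% | 8% |
| Caregivers, 9 scores | 0.5 | 29% | about 16% |

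With 5 caregivers instead of 10, the 13-score figure for any significant result at correlation 0.5 is 41%.

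**Other alphas**, 13 independent tests, any direction: 1 − 0.99^13 = 12.3% at 1%, and 1 − 0.90^13 = 74.6% at 10%.

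**The case against.** The strongest reply is that this is a small, non-randomised pilot that says so. It disclaims power, sets no success criterion and makes no efficacy claim. SAP sections 8.2.2 and 9 also commit to descriptive statistics for all outcomes, a table of mean scores for each measure and a figure with individual data. An unfavourable score therefore cannot simply disappear from the report. That much stands, and it limits the harm. It does not settle the point: lack of power concerns missed effects, and nothing in either document says how a p-value below 0.05 is to be read.

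Three further objections are fair:

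- **The count of 13 is inferred.** The SAP describes subscales and domains but does not say that each is tested. A reader might take 13 separate tests as the stated plan; the documents support 8 listed endpoints, with 13 as a plausible reading. The point survives on 8.
- **Survivors and caregivers can be seen as two families.** They are analysed separately, so the per-group figures (8% and about 16% for a false improvement) are as relevant as the pooled one.
- **Unadjusted 95% intervals carry the same multiplicity** if readers only check whether zero is excluded. This is correct, so the fix has to rule out that use.

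A reader might also infer that a false improvement is about 40% likely. It is not. The 40% counts significant results in both directions. For improvement alone, no correlation gives more than about 28% at a 5% level. Nor do the caregiver findings rest wholly on these tests, since caregivers also complete the PSSUQ and an interview.

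**Conclusion.** The point holds as a mismatch between aim and method. The secondary change endpoints go to unadjusted omnibus tests without an alpha, an order, an exploratory label or an interval, in a study that sets out only to estimate and disclaims power for these outcomes. At an assumed 5% per test and a between-score correlation of 0.5, a false improvement somewhere among the secondary scores has a chance of about one in six (8 tests) to a little under one in four (13 scores). A false significant result of either sign has a chance of about 30% to 40%.

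The alpha, the correlation and the split into subscales and domains are assumptions, because the documents give none of them. The gap is not fatal to a usability pilot. It is worth closing because the results are meant to inform a later trial and closing it is cheap.

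**What to change.** In SAP 5.2 and 8.2.2:

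1. Call all secondary change endpoints exploratory.
2. State which scores are analysed: whether HADS is taken as two subscales and WHOQOL-BREF as four domains.
3. Make the planned output the change from baseline to post-intervention (the stated endpoint), and also to the 1-month follow-up, with a 95% confidence interval for every score, all in one table.
4. State that the intervals are not adjusted for multiplicity, and that no claim of effect rests on p < 0.05 or on an interval that excludes zero.

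If the sponsor prefers to keep p-values for inference, Holm within each group is an option. With 13 scores the first steps are 0.05/4 = 0.0125 in survivors and 0.05/9 = 0.0056 in caregivers. The SAP should then say that control is per group; across two independent groups the bound is 1 − 0.95² = 9.75%. Such thresholds leave little power with 5 to 10 caregivers, so this is a trade-off and not a requirement.

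The cost is SAP wording and one results table, with no new data or participants. The downside is fewer nominally significant results to report, which is consistent with what section 7 already says about power.

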Based on the feedback received by the users, recommendations to modify the content of the videos or the exercises, or the website will be drafted. Based on those recommendations, modifications will be made to the online mindfulness program. If warranted, the testing phase will be replicated with up to a second cohort of 10 participants (5 stroke patients and 5 caregivers).

Ethical considerations

Informed consent

Prior to providing informed consent, all participants (stroke survivors and caregivers) will be fully informed of the procedures involved and requirements for participation in the study. Participants will also be informed of the voluntary nature of participation in the project and the option to withdraw at any time without jeopardy. At the first online meeting, each participant will be asked to read the consent form at his or her own pace. A member of the research team will also explain every element of the consent form and answer any question or concern from the potential participant. Participants will be asked if they understand the nature of the study

and the procedures that will be employed. Then, participants will provide written consent on the REDCap platform should they agree to participate. A copy of the consent form will be printed, signed by the principal investigator, scanned and return to each participant by email. The HIPAA compliant Zoom platform will be used for all meetings.

Participant recruitment

A webpage was created using the Southern California Clinical and Translational Science Institute (CTSI) Clinical studies directory. The link to this webpage will be shared on social medias using a recruitment flyer. Specifically, stroke survivors support group will be targeted (e.g., Stroke Association of Southern California, American Heart Association Support Network). Interested individuals will be encouraged to contact a member of the research team. A member of the research team will contact potential participants to confirm eligibility, explain in more details the research project and answer questions. If difficulty arise with recruitment, participants will also be recruited by phone from an existing IRB-approved database, Registry for Aging and Rehabilitation Evaluation-RARE (HS-11-00413). Phone recruitment will be done using a phone script.

Participant privacy and data confidentiality

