All information collected during this study will be coded in order to assure confidentiality and each participant will be assigned a random unique identification code. Once transcribed and verified for accuracy, the recordings of the semi-structured interviews will be destroyed. Electronic data will be stored on a secured drive and access to the drive will be password protected. Data will be stored for a period of seven years following the end of the study, after which, they will be destroyed. Only the members of the research team will have access to the data. The data identifier will be stored in a different location than the data generated during the study.

Potential risks and procedures for minimizing risks

The risks associated with this study are minimal and there are no expected adverse events. Risks include surveys or interview questions that may make participants feel uneasy or embarrassed, and a breach of confidentiality. During any self-reported or interview question, participants will be allowed to skip or stop answering any questions they wish not to. The HIPAA compliant REDCap platform will be used to obtain informed consent and collect all patient-reported outcomes (coded surveys). No identifier will be collected in REDCap. Study investigators will protect data against the privacy by storing data in locked cabinet, in password protected computers and files, and by using coded identifiers. If a participant scores over 11/21 on the HADS scale for depression and anxiety or if they experience any inconvenience during the study, they will be directed to their primary family physician to ensure they are receiving proper referral to mental health care.

Plan to disseminate findings

It is anticipated that the results from this study will be disseminated in a peer-review publication and at local, national and/or international conferences. To facilitate the knowledge

translation for students doing stroke research, the results will be presented at the Biokinesiology and Physical Therapy Division seminars at the University of Southern California.

References

Alexander, C. N., Langer, E. J., Newman, R. I., Chandler, H. M., & Davies, J. L. (1989). Transcendental meditation, mindfulness, and longevity: an experimental study with the elderly. *Journal of Personality and Social Psychology*. <https://doi.org/10.1037/0022-3514.57.6.950>

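### The three-visit ANOVA drops a completer who misses only the 1-month follow-up, although the primary SIS endpoint is set at post-intervention

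*SAP*

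**What the plan says.** The analysis text in SAP section 8 (printed under 8.2.2) gives one inferential method for the scales: in each group, "differences prior to, after the mindfulness program and at 1-month follow-up will be assessed using a repeated measure analysis of variance (ANOVA"). The one fallback reads "If data normality is violated, data will be transformed, or non-parametric statistics will be substituted". It is triggered by non-normality, not by missing values. On software the SAP says "JASP version 0.14.1. will be used for all statistical analysis" and gives no setting for missing data.

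SAP 5.2 sets the primary endpoint in stroke survivors as "Change in Stroke Impact Scale (SIS): quality of life and impact of stroke (primary, post-intervention"). SAP 6.3, Table 1, puts the three visits at target days 1, 22 and 52, so post-intervention means Day 22. SAP 8.2.1 defines the Full Analysis Population as "All participants who complete the intervention"; attending the 1-month follow-up is not a condition.

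In its ethics section the protocol gives participants "the option to withdraw at any time without jeopardy" (Informed consent) and says that "participants will be allowed to skip or stop answering any questions they wish not to" (Potential risks and procedures for minimizing risks).

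From section 4.1 onward the SAP has no rule for a missed visit, no mixed model, and no separate comparison of Day 1 with Day 22.

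**The concern.** Three parts of the SAP do not fit together. The population admits everyone who completes the program, and the primary endpoint needs Days 1 and 22, but the test needs Days 1, 22 and 52. Whether a person counts in the test of short-term change then depends on whether they respond a month later.

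Two things are at stake. One is precision, in a group so small that each person matters. The other is selection: if people who gained less are less likely to return at Day 52, the people left in the ANOVA show a larger Day 22 gain than the people who were observed at Day 22. SAP objective 2 is to estimate short-term impact, and the protocol wants the results to guide a later intervention study. An inflated estimate would carry into that planning.

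**Working it through.** **Figure in the plan.** The SAP's 10 stroke survivors (section 7) come from no formula. There is no alpha, power, effect size, SD or dropout rate, so there is nothing to reproduce.

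**Inputs from the documents.** Three visits (SAP 6.3), and a final analysis once 10 stroke survivors have completed the intervention and qualitative saturation is reached (SAP 8.1).

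**Assumptions.** All 10 completers give a Day 22 score. The analysis waits for the Day 52 visits, which SAP 8.1 does not say. Loss between Day 22 and Day 52 is 10-20%; the documents give no rate.

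**Step 1: what the method keeps.** With 10 people and two missing only Day 52, the observed values number 10 × 3 − 2 = 28. A standard repeated-measures ANOVA routine rejected such data as unbalanced. It ran only after both people were removed at every visit, leaving 8 × 3 = 24 values. Error degrees of freedom, (n − 1)(3 − 1), fall from 18 to 14. A random-intercept mixed model on the same data used all 28 values. A Friedman-type fallback would also need complete blocks.

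**Step 2: how many people.**
- Entering the ANOVA: 10 × 0.9 = 9, or 10 × 0.8 = 8.
- Chance that at least one of the 10 is dropped: 1 − 0.9^10 = 65%, or 1 − 0.8^10 = 89%.

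**Step 3: precision of the Day 22 change.** The 95% half-width for a mean paired change, in SDs of the change, is t(0.975, n − 1)/√n:

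| n | half-width |
|---|---|
| 10 | 0.715 |
| 9 | 0.769 |
| 8 | 0.836 |

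The interval is 0.769/0.715 = 1.08 to 0.836/0.715 = 1.17 times as wide. This measures what losing people costs; it is not the ANOVA's pooled-error interval. For a group of 5, the lower end of the protocol's range, losing one person takes it from 1.242 to 1.591.

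**Step 4: bias.** If a fraction f of those seen at Day 22 miss Day 52, then

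complete-case mean − mean of all observed = f × (mean of retained − mean of lost).

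With f = 0.1-0.2, each 1 SD by which those lost did worse adds 0.1-0.2 SD to the estimate.

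A simulation shows the same thing under assumed values: 10 people, SD 1 at each visit, correlation 0.6 between visits, true Day 22 change 0.5, and loss likelier after a poor change. About 7.9 people remained on average. The mean Day 22 change was 0.66 in complete cases and 0.50 in everyone observed at Day 22, in units of the SD at one visit.

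**Step 5: does the remedy recover it?** If everyone has Days 1 and 22, a mixed model with a separate mean for each visit returns the observed Day 22 mean change whatever happens at Day 52. A paired contrast on those two visits does so by construction.

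**The case against.** The best reply is that this is a non-randomized usability pilot which says it is not powered for these outcomes, that the SAP nowhere says it will discard incomplete records, and that it already plans descriptive summaries. Much of that stands. Complete-case analysis follows from the method named and is not a sentence in the SAP. No confirmatory claim is at risk.

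A reader might also infer more than the documents support:

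- **That Day 22 scores disappear altogether.** They do not. SAP section 9 promises n, mean and SD for continuous variables and a figure with individual data, and a Day 22 score can appear in both. Only the test loses it. What is not promised is the n entering each ANOVA, so the table and the test may rest on different people.
- **That as few as six survivors would be left.** Taking 10 starters with 10-20% loss before Day 22 and again after it gives 10 × 0.8 × 0.8 = 6.4 to 10 × 0.9 × 0.9 = 8.1. But SAP 8.1 waits for 10 completers. A group of 5 falling to about 3 (5 × 0.8 × 0.8 = 3.2) likewise includes people with no Day 22 score, whom no model could keep in an observed Day 22 result.
- **That the protocol expects gaps.** It grants the rights to withdraw and to skip questions and gives no rates. Under Data collection it says a researcher guides participants through the questionnaires, which should limit accidental skips.
- **That one skipped item removes a person.** This happens only if it voids the score. The SAP does not give the scoring rules for skipped items, so that is a missing detail and not a shown loss.

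None of this answers the mismatch itself. The non-normality fallback does not address it, and the descriptive output does not change who is in the test.

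**Conclusion.** The point holds in this limited form: a completer with Day 1 and Day 22 scores is excluded from the only inferential test because of a visit that the primary endpoint does not use. For the survivor group the cost in precision is modest, a half-width 8-17% wider under the assumed 10-20% loss after Day 22. The possible bias depends on why people miss follow-up, which the documents cannot tell us. The simulated 0.66 against 0.50 illustrates its direction and is not a forecast. If nobody misses Day 52, the problem does not arise.

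The effect is on the impact estimates under objective 2. The change is still worth making before analysis, because it is cheap and removes the dependence of the Day 22 result on Day 52 attendance.

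**What to change.** In SAP section 8, for each group and each score, replace the repeated-measures ANOVA with a linear mixed model: visit as a categorical fixed effect, a random intercept for participant, all observed visits included, and a small-sample degrees-of-freedom correction. Keep the existing plan for non-normal data.

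At minimum, keep the ANOVA and add a Day 1 to Day 22 paired contrast on everyone with both values, with a signed-rank test if the changes are not normal.

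In either case, report the n entering each test beside its result. A sentence naming each instrument's scoring rule for skipped items would be useful, but the point does not rest on it.

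The cost is SAP wording and slightly more analysis work, with no new data. Check that the named software version fits the model with the chosen correction, or amend the software sentence. The mixed model assumes that missingness is explained by the observed scores (missing at random), which should be stated.

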Phase 2) A testing phase will be conducted remotely for both technical and clinical verification with 5-10 stroke survivors and 5-10 caregivers. Self-reported questionnaires about psychological well-being will be administered prior to and after the participation to the program and at a 1-month follow-up. After the program, a usability questionnaire and a semi-structured interview will be conducted to assess the usability of the mindfulness program and gather participants' feedback. For each group, differences prior to and after the mindfulness program will be assessed using a repeated measure analysis of variance. The transcribed verbatim of the semi-structured interview will be analyzed independently using thematic content analysis by 2 members of the research team.

Phase 3) Based on the results from Phase 2, modifications will be made to the online mindfulness program. If warranted, the testing phase will be replicated with up to a second cohort of participants.

This project will lead to the development of an online mindfulness program suitable for stroke survivors and their caregivers to improve quality of life and psychological well-being. This project will help guide the development of a planned intervention study.

Background

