5.1 Study Objectives

1. To pilot test the online mindfulness program with potential users to evaluate the acceptability, ease-of-use, and satisfaction.
2. To estimate the potential impact on quality of life, anxiety, depression and sleep quality in the short term.
3. To obtain a final version suitable for individuals who have had a stroke with a wide range of impairments and their caregivers.

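### The SAP lets an unspecified normality judgement in 5-10 people pick each score's analysis, and it plans no paired change with SD and confidence interval, which the estimation aim needs

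*SAP*

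**What the plan says.** The analysis text in SAP section 8 (after 8.2.2) plans, within each group, a repeated-measures ANOVA over baseline, post-intervention and 1 month. It then adds: "If data normality is violated, data will be transformed, or non-parametric statistics will be substituted". Neither document gives a normality test or threshold. Neither says whether raw scores, changes or residuals are checked, names a transformation or a substitute test, or puts the two options in order.

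On size, SAP section 7 states: "A convenience sample of 10 stroke survivors is targeted to capture the relevance, feasibility and usability of the Mindfulness Program". Section 8.1 times the final analysis for when "a sample of 10 stroke survivors have completed the intervention". The SAP sets no caregiver number. The protocol abstract plans "5-10 stroke survivors and 5-10 caregivers".

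On purpose, the second objective in SAP 5.1 is: "To estimate the potential impact on quality of life, anxiety, depression and sleep quality in the short term". SAP section 7 adds: "This study is not powered to detect differences in quality of life or psychological well-being". No significance level is stated.

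On reporting, section 8 gives mean and SD for normal data and median and IQR for skewed data. Section 9 gives mean and SD for all continuous variables, plus a figure with individual values for each measure. SAP 5.2 words the quantitative endpoints, other than usability, as changes, and labels them post-intervention. No section asks for the SD of those changes or for a confidence interval.

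**The concern.** Two analysts who both follow this text could analyse the same score differently and report different p-values. The choice would rest on a judgement about distribution shape made in very few people, where a formal check is weak and also flags some normal scores by chance. The wording also does not stop the choice between replacements being made after both results are known.

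The larger cost is to the second objective. The protocol (Methods, Phase 2) says the measures are to guide a future intervention study. That calls for the size of the within-person change, its SD and its uncertainty, on the scale of the questionnaire and for every score. An ANOVA p-value does not supply these, and a log-scale or rank analysis moves further from them.

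**Working it through.** **Inputs from the documents.** Three visits (SAP 5.2 and Table 1); 10 stroke survivors (SAP 7 and 8.1); 5-10 per group (protocol abstract). HADS subscales have 7 items scored 0-3, so they run 0-21 (SAP 6.3). The plan has no alpha, SD, effect size or computed sample size, so there is no figure to reproduce.

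**Assumptions not in the documents.** Shapiro-Wilk at 5% as the normality check, tests at 5%, within-person correlation 0.6 on the underlying normal scale, and no true change over time. There were 4,000 simulated groups per cell, so the simulation error near 5% is √(0.05 × 0.95 / 4000) ≈ 0.35 percentage points.

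**Step 1: how often the check flags a score (%).**

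| Shape | n=5, one visit | n=10, one visit | n=5, any of 3 visits | n=10, any of 3 visits |
|---|---|---|---|---|
| Normal | 4.3 | 4.5 | 13.9 | 14.9 |
| Lognormal, log-SD 0.5 | 9.5 | 25.6 | 25.2 | 54.3 |
| Skewed 0-21 score | 15.4 | 32.6 | 37.6 | 65.1 |
| Exponential | 16.0 | 45.5 | 38.6 | 78.3 |
| Lognormal, log-SD 1 | 23.2 | 61.1 | 50.8 | 91.3 |

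For the three less extreme skewed shapes, one visit misses 100 − 16.0 = 84.0% to 100 − 9.5 = 90.5% at n=5, and 100 − 45.5 = 54.5% to 100 − 25.6 = 74.4% at n=10. A separate run flagged 10-17% and 25-44%, that is, missed 83-90% and 56-75%. The two agree closely. The most extreme shape is missed 76.8% and 38.9% of the time. If ANOVA residuals are checked instead, detection is about 2% at n=5 and 12-49% at n=10.

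**Step 2: normal scores switched by chance.** With three independent checks at 5%, 1 − 0.95³ = 0.143. The simulated values are 13.9-14.9%.

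**Step 3: false positives under no change (%).** The last column assumes that, after a flag at any visit, the analyst takes the smallest p-value among log ANOVA, square-root ANOVA and Friedman.

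| n | Shape | ANOVA, never switched | Switch, Friedman fixed | Switch, log fixed | Switch, best of the replacements |
|---|---|---|---|---|---|
| 5 | Normal | 4.4 | 4.3 | 4.4 | 4.6 |
| 5 | Four skewed shapes | 2.4-3.7 | 3.3-3.9 | 3.4-4.1 | 4.2-4.6 |
| 10 | Normal | 4.4 | 4.3 | 4.2 | 4.5 |
| 10 | Lognormal, log-SD 0.5 | 3.6 | 4.0 | 3.9 | 4.8 |
| 10 | Skewed 0-21 score | 4.4 | 4.7 | 4.9 | 6.4 |
| 10 | Exponential | 4.2 | 5.3 | 6.0 | 8.4 |
| 10 | Lognormal, log-SD 1 | 3.2 | 4.4 | 4.8 | 7.2 |

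Two further runs at n=10 on skewed scores gave 6.0-6.9% and 6.4-7.8% for the favourable choice. About 6-8% is a fair summary, although one mildly skewed shape above shows no rise past 5%. At n=8 the favourable choice gave 5.4-7.7% on skewed scores. Over n = 5, 8 and 10, ANOVA never switched gave 2.4-5.4% and Friedman used throughout gave 3.7-4.9%.

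**Step 4: why score SDs at each visit do not give the SD of change.** SD of change = √(s₀² + s₁² − 2·r·s₀·s₁). With equal SDs s this is s·√(2(1 − r)). The documents give no r. Over an assumed range:
- r = 0.3: √1.4 = 1.18 s
- r = 0.6: √0.8 = 0.89 s
- r = 0.8: √0.4 = 0.63 s

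The variance of change therefore differs by a factor of 1.4 / 0.4 = 3.5 across that range, and the planned summary tables would not settle it.

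**Step 5: what an interval would show.** The 95% half-width is t(n−1) × SD of change / √n. At n=5 it is 2.776 / 2.236 = 1.24 SDs of change. At n=10 it is 2.262 / 3.162 = 0.72.

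**The case against.** The strongest reply is that this is a non-randomized pilot that disclaims power, sets no alpha and hangs no decision on a p-value, so a loosely worded fallback does little harm. That stands, and it limits the severity.

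A reader might infer three stronger claims that the documents and the working do not support.

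- **That the switch cannot work at these sizes.** Compared like for like at n=10, a check at any of three visits flags skewed scores 54-91% of the time, against 14.9% of normal ones. Missed skew also costs little in false positives, because the unswitched ANOVA was at or below nominal on skewed scores.
- **That it inflates error across 5-10 people.** At n=5 the favourable choice after a flag stayed at 4.2-4.6%. With one fixed replacement the range over all cells was 3.3-6.0%. The SAP does not say the better result will be taken, so the open choice is the source of any inflation, not the switch itself. If the unswitched ANOVA also stayed in the pool and the smallest p-value were reported, the rate would be 5.9-9.6%, but that goes beyond the sentence as written.
- **That it removes means and SDs for some scores.** Section 9 promises them for every continuous variable. The switch sentence concerns the test. The SD of change and the interval would be missing without it too.

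Two further objections also hold. The SAP names no formal normality test, so the rates depend on assuming one. And n=5 is not the SAP's case for stroke survivors, whose target is 10; it comes from the protocol's range and matters mainly for caregivers.

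One could also argue that endpoints worded as changes imply change summaries. But section 9 speaks of mean scores, and under section 8 a change judged skewed would be given as median and IQR. Neither section provides an interval.

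**Conclusion.** The point holds in a limited form. The SAP lets an undefined normality judgement, unreliable in groups of 5-10, select each score's analysis, and it leaves the replacement open. The cost in false positives is modest and conditional: about 6-8% at n=10 if the more favourable replacement is picked, none at n=5, and little with one replacement named in advance. In the cases simulated, the switch was not needed to protect the ANOVA's error rate.

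The more useful finding is that the plan does not specify the SD of paired change or any confidence interval, although its objective is to estimate impact.

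These sizes rest on Shapiro-Wilk at 5%, correlation 0.6 and the shapes listed. Visual judgement would have unknown rates. Missing follow-up, non-sphericity and a true time effect were not examined. Severity is minor to moderate: it affects how exploratory results are read and reused, not a confirmatory claim.

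**What to change.** 1. For every score, whatever its distribution, report the mean paired change from baseline to post-intervention (the primary time point) and to 1 month, with the SD of change and a 95% CI on the original scale. Show the median change and the planned individual plots alongside.
2. Replace the switch sentence with one pre-named test for all scores, for example the planned repeated-measures ANOVA or Friedman. Label it exploratory, and show any other method only as a sensitivity analysis.
3. Align the descriptive rules in sections 8 and 9, which now differ for skewed continuous variables.

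A paired permutation test is optional and not needed. Its two-sided p-value cannot fall below 2/2⁵ = 0.0625 at n=5. Testing both changes per score without adjustment gave at least one false positive in 8.7-9.2% of simulated groups at n=10, more than the 6-8% at issue here.

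The cost is SAP wording and slightly more reporting, with no new data or participants. The t-based intervals will be wide, and only approximate for skewed scores.
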